6.13.3 Modification of Background Therapy

During the first 12 weeks of the OLE study, background MTX (all subjects) and sulfasalazine and/or hydroxychloroquine (for subjects assigned rescue medication starting at Week 14 in the core studies) should remain unchanged and may be adjusted only for safety reasons according to Investigator discretion (see Appendix 1 [Section 13.1] for guidelines on MTX dose reduction). Subjects from CL04041025 are exempt from this restriction, and have their background therapy may be adjusted at the Investigator's discretion.

For subjects who receive background sulfasalazine and/or hydroxychloroquine, periodic safety evaluations for toxicity resulting from sulfasalazine and/or hydroxychloroquine should be undertaken as per the drug label and local guidelines. The maximum allowed doses of sulfasalazine and hydroxychloroquine are:

• Sulfasalazine: 3 g per day

• Hydroxychloroquine: 400 mg per day

Dose tapering of background oral corticosteroids and NSAIDs (if applicable) is permitted according to Investigator discretion, but the dose should otherwise remain unchanged unless the Investigator changes the dose for safety reasons.

After the first 12 weeks of the OLE study (i.e., after Visit 4 [Week 36]), the Investigator may modify background therapy, if deemed appropriate, per local guidelines. Modifications to background therapy may include:

- Modification of MTX for all subjects
- Modification of sulfasalazine and/or hydroxychloroquine for subjects assigned rescue medication starting at Week 14 in the core studies
- Sulfasalazine and/or hydroxychloroquine may not be prescribed to subjects who did not receive these rescue medications in the core studies.
- Modification of oral corticosteroids (including initiation of doses ≤10 mg/day of prednisone or equivalent)
- Administration of IM or IV corticosteroids
- Modification of NSAIDs (including switching of NSAIDs)

6.14 Medical Treatment for Subjects after End of Treatment Period

After completion of the 82-week, open-label Treatment Period, or after premature discontinuation of study treatment, subjects will enter the Safety Follow-Up Period. It is the responsibility of the Investigator to choose adequate treatment.

7. EFFICACY, SAFETY, PHARMACOKINETIC, AND HEALTH OUTCOME ASSESSMENTS

7.1 Efficacy Assessments

7.1.1 American College of Rheumatology 20%/50%/70% Response Criteria

ACR20/ACR50/ACR70 will not be calculated by the Investigator during the course of the study, but will be computed in the statistical database for analysis purposes.

The number of subjects who achieve an ACR20, ACR50, or ACR70 response at various time points will be calculated. The calculations are based on a \geq 20%, \geq 50%, and \geq 70% improvement from baseline in the SJC assessed in 66 joints and in the TJC assessed in 68 joints; and a \geq 20%, \geq 50%, and \geq 70% improvement from baseline in at least 3 of the 5 remaining core set measures:

- Patient Global Assessment of Disease Activity (VAS)
- Patient Assessment of Pain (VAS)
- HAQ-DI
- Physician Global Assessment (VAS)
- Level of acute phase reactant (CRP or ESR, using level of CRP in this study)

7.1.2 66-68 Joint Assessment

The 66-68 joint assessment evaluates 66 joints for swelling and 68 joints for tenderness and pain on motion. The hip joints can be assessed for tenderness, but not for swelling. The following joints are included:

• Temporomandibular, sternoclavicular, acromioclavicular, shoulders, elbows, wrists, interphalangeal (IP) on digit 1, distal interphalangeals on digits 2 to 5, proximal interphalangeals (PIP) on digits 2 to 5, metacarpophalangeal (MCP) on digits 1 to 5, hips (tenderness only), knees, ankles and tarsus, metatarsals, IP on toe 1, PIP on toes 2 to 5, and metatarsophalangeals (MTP) on toes 1 to 5.

As noted in Table 1, the joint assessor will be independent to the rest of the study team. An independent joint assessor, blinded to other study assessments as well as the dosing regimen, will be identified at each study site to perform the SJC and TJC. To ensure consistent joint evaluation throughout the study, individual subjects should be evaluated by the same joint assessor as in the core studies for all study visits, whenever possible.

Artificial, missing, and ankylosed joints are excluded from both tenderness and swelling assessments. If joints are missing or not able to be assessed, the number of joints will be weighted by the actual number of assessable joints, and the missing or not assessable joints should be marked as "not assessed" for all subsequent joint assessments for the remainder of the study. If a subject receives IA corticosteroids or IA hyaluronic acid (see Section 6.13.2), any treated joints should be omitted from all subsequent joint assessments and should be rated with their pre-injection status for the remainder of the study.

7.1.3 Patient Global Assessment of Disease Activity (Visual Analog Scale)

Subjects will assess the overall disease activity by responding to the following:

• Considering all the ways in which illness and health conditions may affect you at this time, please make a mark below to show how you are doing, using a 100 mm VAS where 0 is "very well" and 100 is "very poorly".

7.1.4 Patient Assessment of Pain (Visual Analog Scale)

Subjects will rate their short-term arthritis pain by responding to the question:

• How much pain are you experiencing because of your illness AT THIS TIME? Place a vertical (I) mark on the line to indicate the severity of the pain, using a 100 mm VAS where 0 is "no pain" and 100 is "severe pain".

7.1.5 Physician Global Assessment (Visual Analog Scale)

The Investigator will rate the overall status of the subject for the day of the visit, with respect to RA signs and symptoms and the functional capacity of the subject. The Investigator will respond to the following:

• Mark an X on the line below to indicate disease activity (independent of the patient's self-assessment). A 100 mm VAS will be used, where 0 is "no disease activity" and 100 is "maximal disease activity".

7.1.6 Disease Activity Score 28-Joint Count (C-Reactive Protein)

The DAS28 (CRP) will not be calculated by the Investigator during the course of the study, but will be computed in the statistical database for analysis purposes.

The DAS28 (CRP) will be calculated using the SJC (28 joints), TJC (28 joints), CRP level, and the Patient Global Assessment of Disease Activity (VAS) (in mm) according to the following formula:

DAS28 (CRP) =
$$0.56 \times \sqrt{\text{(TJC)} + 0.28} \times \sqrt{\text{(SJC)} + 0.36} \times \text{lognat (CRP + 1)} + 0.014 \times \text{Patient Global Assessment of Disease activity (VAS)} + 0.96$$

The 28 joints evaluated for the SJC and TJC are as follows:

• Shoulders, elbows, wrists, IP on digit 1, PIP on digits 2 to 5, MCP on digits 1 to 5, and knees

Details of the joint assessment process are provided in Section 7.1.2.

7.1.7 Disease Activity Score 28-Joint Count (Erythrocyte Sedimentation Rate)

The DAS28 (ESR) will not be calculated by the Investigator during the course of the study, but will be computed in the statistical database for analysis purposes.

The DAS28 (ESR) will be calculated using the SJC (28 joints), TJC (28 joints), ESR (mm/hour), and the Patient Global Assessment of Disease Activity (VAS) (in mm) according to the following formula:

DAS28 (ESR) =
$$0.56 \times \sqrt{\text{(TJC)} + 0.28} \times \sqrt{\text{(SJC)} + 0.70} \times \text{lognat (ESR)} + 0.014 \times \text{Patient}$$

Global Assessment of Disease Activity (VAS)

The 28 joints evaluated for the SJC and TJC are as follows:

• Shoulders, elbows, wrists, IP on digit 1, PIP on digits 2 to 5, MCP on digits 1 to 5, and knees

Details of the joint assessment process are provided in Section 7.1.2.

7.1.8 Simplified Disease Activity Index

The SDAI will not be calculated by the Investigator during the course of the study, but will be computed in the statistical database for analysis purposes.

The SDAI will be calculated using the SJC (28 joints), TJC (28 joints), CRP (mg/dL), the Patient Global Assessment of Disease Activity (VAS) (in cm), and the Physician Global Assessment (VAS) (in cm) according to the following formula:

SDAI = SJC + TJC + Patient Global Assessment of Disease Activity (VAS) + Physician Global Assessment (VAS) + CRP

7.1.9 Clinical Disease Activity Index

The CDAI will not be calculated by the Investigator during the course of the study, but will be computed in the statistical database for analysis purposes.

The CDAI will be calculated using the SJC (28 joints), TJC (28 joints), the Patient Global Assessment of Disease Activity (VAS) (in cm), and the Physician Global Assessment (VAS) (in cm) according to the following formula:

CDAI = SJC + TJC + Patient Global Assessment of Disease Activity (VAS) + Physician Global Assessment (VAS)

7.1.10 Health Assessments and Patient-Reported Outcomes

The PROs that will be utilized for efficacy assessments are discussed in this section.

7.1.10.1 Health Assessment Questionnaire – Disability Index

The HAQ-DI is a patient-reported questionnaire that provides an assessment of the impact of the disease and its treatment on physical function. The HAQ-DI assesses the degree of difficulty experienced in 8 domains of daily living activities using 20 questions. The domains are dressing and grooming, arising, eating, walking, hygiene, reach, grip, and common daily activities, and each domain (activity) consists of 2 or 3 items. For each question, the level of difficulty is scored from 0 to 3 where 0 = without any difficulty, 1 = with some difficulty, 2 = much difficulty, and 3 = unable to do. Each category is given a score by taking the maximum score of each question (i.e., question in each category with the highest score for that category).

If the maximum score is 0 or 1, but a device related to that category is used, or help from another person is provided for the category, then the category score is increased to 2. If the category score is already a 2 (or above), the score in that category remains 2 with or without any aids or device use. If the subject does not provide an answer for any questions within a category, no score will be provided for that category. The HAQ-DI will be calculated by dividing the sum of the category scores by the number of categories with at least 1 question answered. If fewer than 6 categories have responses, no disability score will be calculated.

The HAQ-DI will also include patient assessments of pain and health on a scale of 0 to 100.

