4.2 Efficacy Endpoints

For the efficacy endpoints, comparison will be made with Core Baseline values (i.e., Week 0 baseline values in the core study) and OLE Baseline values (i.e., Week 24 baseline values in the OLE study) for most parameters, as defined in Section 9.4.1. For subjects from Study CL04041025 who initiate OKZ treatment at Week 16 of the core study after having completed 16 weeks of placebo treatment, changes from the last pre-OKZ value will also be summarized.

The following efficacy endpoints will be evaluated:

- Proportion of subjects achieving an ACR20, ACR50, and ACR70 response who remain on randomized open-label treatment and in the study, assessed at all applicable time points
- Proportion of subjects with Simplified Disease Activity Index (SDAI) ≤3.3 remission, who remain on randomized open-label treatment and in the study, assessed at all applicable time points

- Proportion of subjects with Disease Activity Score 28-joint count (DAS28) low
 disease activity (based on DAS28 C-reactive protein [CRP] <3.2), who remain on
 randomized open-label treatment and in the study, assessed at all applicable time
 points
- Change from baseline over time in DAS28 (CRP), assessed at all applicable time points
- Change from baseline over time in the measure of physical ability based on Health Assessment Questionnaire-Disability Index (HAQ-DI), assessed at all applicable time points
- Proportion of subjects with improvement from baseline in HAQ-DI score ≥0.22, who
 remain on randomized open-label treatment and in the study, assessed at all applicable
 time points
- Change from baseline over time in the scores for the following patient-reported outcomes (PRO) measures, assessed at all applicable time points:
- Short Form-36 (SF-36) Physical Component Summary (PCS) and Mental Component Summary (MCS) total scores
- European Quality of Life-5 Dimensions (EQ-5D)
- Work Productivity Survey-Rheumatoid Arthritis (WPS-RA)
- Functional Assessment of Chronic Illness Therapy-Fatigue Scale (FACIT-Fatigue)
- Change from baseline over time in SDAI and Clinical Disease Activity Index (CDAI), assessed at all applicable time points

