9.4 Statistical Methods

This section provides a high-level description of the analyses planned in this study. Details of any analysis, interim or final, will be specified in the SAP, to be written and finalized prior to database lock. The statistical analysis will be performed by R-Pharm International's designee. All statistical analyses will be conducted using SAS® version 9.2 or higher for Windows.

All data collected in the clinical database will be presented in subject data listings.

Data collected after the modification of background therapy (as described in Section 6.13.3) will be used in all analyses.

Data collected during the core studies for subjects enrolled in the OLE study may be programmatically combined with the OLE study database for selected analyses.

All analyses of safety and efficacy will be descriptive; no inferential analyses will be performed.

Continuous endpoints will be summarized using descriptive statistics such number of available values (n), mean, median, minimum, maximum, and standard deviation in each treatment group and overall, as appropriate. Categorical endpoints will be summarized by the number and percentage of subjects in each category.

Data will be summarized based on treatment groups reflecting randomized or actual treatment (for efficacy or safety analyses, respectively) during the core and OLE studies as follows:

- a. OKZ 64 mg q4w (OLE): All subjects in the OKZ 64 mg q4w group in the OLE
- b. OKZ 64 mg q2w (OLE): All subjects in the OKZ 64 mg q2w group in the OLE
- c. OKZ 64 mg q4w (core/OLE): Subjects from the OKZ 64 mg q4w group in the core study and continuing on OKZ 64 mg q4w in OLE. For subjects enrolling from the CL04041025 core study, inclusion in the OKZ 64 mg q4w group in the core study will be based on the initial treatment period prior to Week 16 (i.e., placebo subjects re-randomized to receive OKZ 64 mg q4w at Week 16 will not be included in this group).
- d. OKZ 64 mg q2w (core/OLE): Subjects from the OKZ 64 mg q2w group in the core study and continuing on OKZ 64 mg q2w in OLE. For subjects enrolling from the CL04041025 core study, inclusion in the OKZ 64 mg q2w group in the core study will be based on the initial treatment period prior to Week 16 (i.e., placebo subjects

re-randomized to receive OKZ 64 mg q2w at Week 16 will not be included in this group).

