9.4.1 Definition of Baseline

Unless otherwise specified, data will be analyzed for changes from both Core Baseline and OLE Baseline values. The Core Baseline value for each parameter will be defined as the baseline value from the core study (i.e., the last available measurement prior to the first dose

of study treatment in the core study). The OLE Baseline value will be defined as the last available measurement prior to the first OLE dose of study treatment. For subjects from Study CL04041025 who receive placebo through Week 14 and are re-randomized to OKZ starting at Week 16 (groups [g] and [h] as defined in Section 9.4), additional analysis of change from the last pre-OKZ value (prior to the first dose of OKZ at Week 16) will also be performed.

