9.4.7 Analysis of Efficacy Endpoints

Analysis of efficacy endpoints (see Sections 4.2) and PROs (see Section 7.1) will be based on the mITT population. Supportive analyses will also be done using the PP population for the ACR20/50/70, $SDAI \le 3.3$, and DAS28 (CRP) < 3.2 endpoints.

All summaries will be presented by the treatment groups defined in Section 9.4, based on randomized treatment.

All continuous efficacy and PRO endpoints will be summarized at each OLE visit in terms of actual values, changes from Core Baseline values, changes from OLE Baseline values, and changes from the last pre-OKZ values (see Section 9.4.1). All categorical parameters and responder-type endpoints will be summarized in terms of number and percent of subjects in each category by OLE visit. Core Baseline values, OLE Baseline values, and the last pre-OKZ values will also be summarized for reference. Graphical summaries will also be presented for mean actual values over time by treatment group for selected endpoints (e.g., DAS28 [CRP]).

Binary endpoints that are based on changes from baseline (e.g., ACR20) will be analyzed based on changes from Core Baseline values, OLE Baseline values, and changes from the last pre-OKZ values.

Missing efficacy data resulting from missed intermediate visits will be handled as described in Section 9.4.8.

Missing data resulting from early treatment discontinuation will not be imputed, unless otherwise specified. For binary efficacy endpoints, in addition to analyses based on observed data, summaries will also be provided considering all subjects who discontinue the OLE study treatment early as nonresponders at all post-discontinuation scheduled time points.

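### The HAQ-DI scoring rule contradicts itself for a category scored 3; followed literally, it caps every category at 2 and loses all movement between 2 and 3.

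*Combined protocol and SAP*

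**What the plan says.** Section 7.1.10.1 builds the HAQ-DI in steps.

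- For each of 20 questions, "the level of difficulty is scored from 0 to 3", where 3 is the worst level.
- "Each category is given a score by taking the maximum score of each question", that is, the highest item in each of the eight categories.
- A category at 0 or 1 is raised to 2 if a related device or another person's help is used.
- "If the category score is already a 2 (or above), the score in that category remains 2", and this holds with or without aids or devices.
- The index is the sum of the category scores divided by the number of categories answered. At least six are needed.

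The score is used in several places. Section 4.2 lists change from baseline in HAQ-DI and also "Proportion of subjects with improvement from baseline in HAQ-DI score ≥0.22". Section 7.1.1 makes HAQ-DI one of the further ACR measures, where response needs "improvement from baseline in at least 3 of the 5 remaining core set measures" as well as improvement in both joint counts. Section 3.2 has a secondary objective on physical function.

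On baselines, Section 9.4.1 says "The Core Baseline value for each parameter will be defined as the baseline value from the core study", and Section 9.4.7 says binary endpoints of change "will be analyzed based on changes from Core Baseline values, OLE Baseline values, and changes from the last pre-OKZ values". Section 9.4 adds: "Details of any analysis, interim or final, will be specified in the SAP". The documents contain no HAQ-DI derivation other than Section 7.1.10.1.

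**The concern.** Under the maximum rule a category takes the values 0, 1, 2 or 3. The later sentence explicitly includes scores above 2 and assigns them 2. A category at 3 cannot both keep its maximum and be 2. Because the sentence applies with or without aids, the literal reading affects every subject with a category at 3, not only those who use aids.

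If the sentence were programmed as written, the top of the scale would disappear. A category that improves from 3 to 2 and one that worsens from 2 to 3 would both score no change. That would distort mean change, the 0.22 responder proportion and the HAQ-DI component of ACR20/50/70. The distortion has no fixed direction: real improvement can be hidden, and so can real deterioration.

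A second risk arises because change is measured partly against values from the core studies. If those were scored on the full scale and the extension visits with the cap, a category that stays at 3 would appear to improve.

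**Working it through.** The plan states no figure to reproduce, so the two readings were applied to the same category scores.

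**Inputs.** Items 0 to 3, category equal to its highest item, the aid rule and the index formula come from Section 7.1.10.1. The 0.22 threshold comes from Section 4.2 and the ACR 20% criterion from Section 7.1.1. All eight categories are taken as answered unless stated. The profiles below are constructed illustrations without aids, not trial data.

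**Mapping of category maxima 0, 1, 2, 3**

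| | No aid | Aid or help |
|---|---|---|
| Maximum kept | 0, 1, 2, 3 | 2, 2, 2, 3 |
| Literal sentence | 0, 1, 2, 2 | 2, 2, 2, 2 |

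The index maximum is 8×3/8 = 3.0 if the maximum is kept and 8×2/8 = 2.0 under the literal sentence.

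**General relation.** Capping takes one point off the sum for each category at 3. Hence

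capped improvement = true improvement − (categories at 3 at baseline − categories at 3 at the visit)/8.

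**Responder status (improvement ≥0.22).** One category step is 1/8 = 0.125, so two net steps are needed (0.25).

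| Case | Baseline → visit | True improvement | Capped improvement |
|---|---|---|---|
| (a) two 3→2 | 3,3,2,2,2,1,1,1 → 2,2,2,2,2,1,1,1 | 15/8 − 13/8 = 0.25, responder | 13/8 − 13/8 = 0, nonresponder |
| (b) one 3→2, one 2→1 | 3,2,2,2,1,1,1,1 → 2,1,2,2,1,1,1,1 | 13/8 − 11/8 = 0.25, responder | 12/8 − 11/8 = 0.125, nonresponder |
| (c) two 2→1, one 2→3 | 2,2,2,2,1,1,1,1 → 1,1,3,2,1,1,1,1 | 12/8 − 11/8 = 0.125, nonresponder | 12/8 − 10/8 = 0.25, responder |
| (d) two 2→3 | 2,2,2,2,1,1,1,1 → 3,3,2,2,1,1,1,1 | 12/8 − 14/8 = −0.25, worse | 12/8 − 12/8 = 0, no change |

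In (b) and (c) a single category crossing between 2 and 3 changes the status. With seven or six categories answered, one step is 0.143 or 0.167, so two steps (0.286 or 0.333) are still needed.

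**ACR 20% criterion, HAQ-DI component only**

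- Lost: 3,3,2,2,1,1,1,1 → 2,2,1,2,1,1,1,1. True (14 − 11)/14 = 21.4%; capped (12 − 11)/12 = 8.3%.
- Gained: 3,2,2,2,2,2,2,1 → 3,1,1,1,2,2,2,1. True (16 − 13)/16 = 18.75%; capped (15 − 12)/15 = 20.0%.

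**Mean change.** By the general relation, if net moves out of 3 make up a share p of the total category-point improvement, mean improvement is understated by exactly p. For assumed p of 0, 5, 10, 20 or 30% the loss is 0, 5, 10, 20 or 30%. If net movement is into 3, improvement is overstated instead. This restates the algebra; it is not an estimate for the trial.

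**Mixed scoring (assumption).** Suppose the core value is uncapped, the extension value is capped, and nothing truly changes. Then k categories at 3 give a false improvement of k/8: 0.125 for k = 1, and 0.25 for k = 2, which passes 0.22.

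**The case against.** The strongest reply is that the literal reading is not the intended one. The sentence follows the rule for aids, a score of 3 cannot sensibly be said to remain 2, and the natural sense is that aids leave a score of 2 or more alone. That is probably right. It explains the error but does not remove it, since the text names scores above 2 and gives them a value.

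The derivation that will actually be run also cannot be seen. Section 9.4 leaves analysis details to the SAP, which may or may not repeat the sentence, so every consequence is conditional on the sentence being followed. That stands.

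Nothing in the text says that core and extension data are scored differently. Section 5.4.1.1 makes Visit 1 the same visit as core Week 24, with shared assessments done once, and Section 9.4 allows the databases to be combined. Mixed scoring is therefore a reason to check, not evidence of a fault.

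The ACR figures concern one component. HAQ-DI decides an ACR response only when both joint counts qualify and exactly two of the other four measures do, and no flipped ACR response has been shown. That stands too.

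Finally, the stakes are modest. The primary objective is safety, efficacy is secondary, all analyses are descriptive, and the nonresponder review in Section 5.4.1.4 uses joint counts. No error rate, sample size or subject-management decision depends on HAQ-DI.

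**Conclusion.** The concern holds. Section 7.1.10.1 gives two incompatible scores for a category at 3, and the documents contain no other HAQ-DI rule to settle it. If the literal sentence is followed, the scale is shortened by a third (from 3.0 to 2.0), each category moving between 2 and 3 misstates the index by 0.125, and one such category can be enough to change 0.22 responder status in either direction.

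These sizes assume eight scored categories and literal programming. The documents do not show that scores will be capped, and they give no HAQ-DI distribution, so the number of subjects affected is unknown. Confidence is high that the rule is wrong as written; no claim is made about its actual effect on results. It should be corrected because it is an operative rule for two listed endpoints and an ACR component, but it does not touch the primary objective or any inference.

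**What to change.** Replace the sentence in Section 7.1.10.1 with: *If the category score is already 2 or 3, it is left unchanged, with or without aids or devices.* State that the index runs from 0 to 3.

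Confirm in the SAP that Core Baseline, last pre-olokizumab, OLE Baseline and all extension-visit values are derived by this one rule, and check how the core studies scored HAQ-DI. Re-derive from item-level data only if that check finds a difference.

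The cost is one reworded sentence, one stated range and one check of the core-study derivation. No new data are needed.
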